5.3.3 Tumor Assessments

 To be completed every 8 weeks (+/- one week) during first year of treatment and every 3 months (+/- one week) after the first year until patient comes off study

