6.1.3 Methods for Evaluation of Measurable Disease

All measurements should be taken and recorded in metric notation using a ruler or calipers. All baseline evaluations should be performed as closely as possible to the beginning of treatment and never more than 28 days before the beginning of the treatment.

The same method of assessment and the same technique should be used to characterize each identified and reported lesion at baseline and during follow-up. Imaging-based evaluation is preferred to evaluation by clinical examination when both methods have been used to assess the antitumor effect of a treatment.

Conventional CT and MRI. These techniques should be performed with cuts of 10 mm or less in slice thickness contiguously. Spiral CT should be performed using a 5 mm contiguous reconstruction algorithm. This applies to tumors of the chest, abdomen, and pelvis. MRI is also acceptable in certain situations (e.g. for body scans). Scans will be done within 28 days prior to cycle 1 and after that every 8 weeks (+/- 7 days) until end of treatment.

Cytology, Histology. These techniques can be used to differentiate between partial responses (PR) and complete responses (CR) in rare cases (e.g., residual lesions in tumor types, such as germ cell tumors, where known residual benign tumors can remain).

The cytological confirmation of the neoplastic origin of any effusion that appears or worsens during treatment when the measurable tumor has met criteria for response or stable disease is mandatory to differentiate between response or stable disease (an effusion may be a side effect of the treatment) and progressive disease.

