6.1.6 Progression-Free Survival

Progression-free survival (PFS) is defined as the duration of time from start of treatment to time of progression *or death, whichever occurs first.*

Progression is defined as death, radiographic progression as defined in 6.1.4.3, or clinical deterioration attributed to disease progression as judged by the investigator.

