9.2 Sample Size and Accrual

Sample Size: Given null- and alternative-hypothesis proportions of 0.05 and 0.20, respectively, approximately 20 evaluable subjects will signal futility/efficacy with 80-percent power and five percent risk of type-I error. Under these conditions the table below gives the number of evaluable subjects required, the smallest number of patients progression-free at six months to signal efficacy, and the probability of correctly declaring futility.

Design Approach	Sample Size	Responses Signal Efficacy	Probability Correctly Asserting Futility
Minimax	19	>=2	0.75

As may be seen, the minimax approach requires 19 evaluable subjects for this project. If at least two participants are progression-free at six months, then the treatment regimen is considered worthy of further study. Given that result, then, in a separate study to complete stage two of the design, an additional eight evaluable subjects would be run. If at least four of the total of 27 evaluable were progression-free at six months that would be sufficient evidence to reject the null hypothesis of five percent in favor of the alternative hypothesis of 20 percent. The probability of declaring futility when in fact the null hypothesis (viz., 5%) is true is at least 75 percent.

No more than nine patients with PD-L1 CPS = 1-9% who are immunotherapy naïve will be enrolled.

Continuous Monitoring for Excess Toxicity: All participants in trial are monitored for serious toxicity for the duration of their participation in the study. Serious toxicities are given in Section 7. A sequential Pocock-type boundary will inform decisions to continue or stop accrual for excess toxicity, as accrual proceeds (Ivanova, 2005). The table below shows the cumulative number of participants enrolled and the corresponding cumulative number of serious toxicities that will signal the underlying risk of serious toxicity exceeds 33 percent (5% risk of type-1 error).

Threshold Number of Cumulative Toxicities that Signal Excess Toxicity as a Function of Cumulative Number Enrolled*

Cumulative	Threshold Number
Number	Showing Serious
Enrolled	Toxicity to Stop
	Accrual
1	-
2	-
3	-

CONFIDENTIAL

4	4
5	5
6	5
7	6
8	7
9	7
10	7
11	8
12	8
13	9
14	9
15	10
16	10
17	11
18	11
19	12
20	12

^{*} Pocock -type boundary with maximum acceptable probability of toxicity set to 33 percent and type-1 risk of five percent[40].

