9.3 Data Analyses Plans

The primary endpoint (PFS-6) will be calculated at 6 months after the last patient enrolled has started treatment, or at the time of progression of the last patient enrolled, whichever occurs first.

Participants will be characterized on host and demographic factors, with continuous measures given as means or medians and categorical measures given as percents. Consistent with the phase-II nature of the research, we will examine the data in many ways to illuminate future research priorities. We will estimate survival curves for progression-free and overall survival, and attempt to identify systematic differences between those who respond to treatment and those who do not. Survival will be estimated by Kaplan-Meier methods. If assumptions are met, we will model survival using Cox proportional- hazards, eliminating ties by subtracting a small, randomly generated amount from the observed times[41]. As may be indicated, we will transform data to correspond better to analytic requirements, using logit transforms for percent data[42] and log or some other approach for continuous measures. As the goals of these secondary analyses are to inform decisions about future research, no formal statistical hypothesis-testing will be done, probabilities from statistical tests will augment clinical judgment in interpretation, and we will not regard overall, study-wise, error rates for these secondary analyses.

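### Section 9.3 breaks Cox ties at random, so exactly tied event times make exploratory hazard ratios and p-values depend partly on an arbitrary draw; the effect is usually small and free to remove

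*Combined protocol and SAP*

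**What the plan says.** Section 9.3 covers both time-to-event outcomes: "We will estimate survival curves for progression-free and overall survival". If its assumptions are met, a Cox model follows, with ties handled by "eliminating ties by subtracting a small, randomly generated amount from the observed times". No section gives the size or distribution of that amount, a seed, a number of repeats or a deterministic alternative.

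The same section limits the role of these results: "no formal statistical hypothesis-testing will be done, probabilities from statistical tests will augment clinical judgment in interpretation". They are meant to inform decisions about future research.

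Three other places determine how often ties arise:

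- Section 5.3.3 sets tumor assessments: "To be completed every 8 weeks (+/- one week) during first year of treatment".
- Section 6.1.3 gives the same interval and window: "after that every 8 weeks (+/- 7 days) until end of treatment".
- Section 6.1.6 counts PFS from each patient's start of treatment. Besides radiographic progression it counts death as an event, "or clinical deterioration attributed to disease progression as judged by the investigator".

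No section says whether PFS is analysed from actual dates, nominal visit days, weeks or months.

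**The concern.** The Cox partial likelihood uses only the order of the event times. When two patients share an event time, random subtraction creates an order that the data do not contain. Two analysts who follow 9.3 exactly, on the same data, can therefore report different hazard ratios and p-values. Scheduled scans make shared PFS times likely, and the sample is small, so each ordering carries some weight. At stake is the reproducibility of exploratory results that the plan intends to use, p-values included, when judging what to study next.

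**Working it through.** **1. What the primary design uses.** The documents give no figure for the Cox analysis. The nearest stated figure is the 0.75 probability of correctly declaring futility in 9.2 ("Given null- and alternative-hypothesis proportions of 0.05 and 0.20, respectively", "with 80-percent power and five percent risk of type-I error").

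P(at most 1 of 19 | 0.05) = 0.95^19 + 19 × 0.05 × 0.95^18 = 0.377 + 0.377 = 0.755.

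The exact two-stage calculation (stop at 1 or fewer of 19, reject at 4 or more of 27) gives alpha 0.041 and power 0.803, so the stated figures reproduce. The rule counts patients and involves no ordering of event times, so tie handling cannot reach it.

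**2. Why a random order changes the estimate.** Let S be the sum of exp(βx) over the risk set, and let patients A and B have tied events. If A is placed first, the two denominators are S and S − exp(βx_A). If B is placed first, they are S and S − exp(βx_B). These differ whenever x_A ≠ x_B. Efron's method uses S and S − ½[exp(βx_A) + exp(βx_B)], which has one value. Only exact ties matter; dates that are merely close are unaffected, provided the subtracted amount stays below the recording unit.

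**3. Will exact ties occur?** Under the plan's own hypotheses, 80-95% of patients fail by six months: 27 × 0.80 ≈ 22 to 27 × 0.95 ≈ 26. Suppose 22 events are all found at the week 8, 16 and 24 scans. Each window has 15 days, so 45 study days are available. With independent, uniform dates:

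- 22 events: P(no tie) = 45!/(23! × 45^22) ≈ 0.002.
- 15 events (19 × 0.80): P(no tie) = 45!/(30! × 45^15) ≈ 0.07.

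Off-scan deaths and clinical progressions reduce the number of ties but do not abolish them.

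**4. How large is the effect?** No closed formula applies, so it was simulated. Setting A assumes 27 patients split 9 vs 18 on one binary covariate, hazard ratio 0.6, exponential times with median PFS 2 months, progression dated at the next scan, and censoring at 52 weeks. The 2.0-month median is the single-agent pembrolizumab figure in the background; the other values are assumptions.

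| Dating of events | Events tied | Mean seed SD of log-HR | Data sets crossing p=0.05 on seed alone |
|---|---|---|---|
| Nominal scan day | nearly all | 0.09 | about 20% |
| Actual date within ±7 days | 37% | 0.015 | under 1% to 3% |
| As above, 30% of events off-scan | about 25% | about 0.01 | about 1-3% |

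Setting B assumes 19 or 27 patients split about equally, hazard ratio 0.5, median PFS 2 to 3 months, censoring at 540 days, and Uniform(0, 0.01 day) subtracted, with 200 data sets and 200 seeds each:

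| Dating of events | Events tied | Median max/min HR over seeds | Median p-value range | Crossing p=0.05 |
|---|---|---|---|---|
| Nominal scan day | 86-93% | 1.33-1.66 | 0.11-0.24 | 21-39% |
| Actual date within window | 18-40% | 1.01-1.04 | 0.005-0.018 | 0-6% |
| As above, 30% off-scan | 13-25% | 1.00-1.02 | 0.000-0.010 | 1-3% |

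In one illustrative data set (27 patients, nominal days, 1000 seeds) the hazard ratio ran from 0.48 to 0.62 and p from 0.074 to 0.235. Efron's method gave a single answer, 0.54 with p = 0.130.

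**5. Against sampling error.** With 9 vs 18 patients all having events, SE(log-HR) is roughly √(1/9 + 1/18) = 0.41; the simulated value is about 0.45.

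- Seed SD 0.015: √(0.45² + 0.015²) = 0.4502, an increase below 0.1%.
- Seed SD 0.09: √(0.45² + 0.09²) = 0.459, an increase of about 2%.

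**6. Event and censoring on the same day.** If censored times are perturbed too, a patient censored on another's event day may be moved ahead of that event and leave its risk set. If only event times are reduced, events still precede same-day censorings, which is the usual convention. The text fits either reading. Setting A does not test this: censoring on day 364 lies outside the windows around week 48 (days 329-343) and week 56 (days 385-399).

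**The case against.** The strongest reply is that the effect is too small to matter. PFS runs from each patient's own start and scans have a window, so clustering around scans is not the same as exact ties. Deaths and clinical progressions fall on other days. With actual dates the random ordering adds almost nothing to the sampling error of 27 patients. The plan does no formal testing, so crossing 0.05 is a yardstick rather than a decision. A recorded seed would make any run repeatable. The covariate split and hazard ratio are assumed, since 9.3 names no covariates. Overall survival was not simulated, and death dates are not linked to scans.

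Most of this stands and sets the size of the point. It does not defend the method. A recorded seed makes one arbitrary order repeatable without making it less arbitrary, and 9.3 does not call for one. The plan still lets p-values inform judgment.

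Two stronger readings are tempting. A reader might infer that progression is seen only at scans and that about a fifth or more of analyses would change with the seed. Section 6.1.6 contradicts the first part, and the second requires every event to be dated to its nominal visit, which no section says. A reader might also infer that event-censoring order is certainly disturbed; the wording of 9.3 does not settle that.

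**Conclusion.** The point holds as a minor one. Where event times tie exactly, the method in 9.3 makes the Cox hazard ratio and p-value depend partly on an arbitrary random order, and 8-week scans make some exact ties very likely. With actual dates inside the scan window the consequence is usually negligible beside sampling error, as the window rows in both tables show. It would be material if PFS were coded to nominal visits, or to units coarse enough to create as many ties, and the documents leave that open.

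These sizes rest on one binary covariate, exponential times, hazard ratios of 0.5-0.6 and median PFS of 2-3 months. The existence of the dependence does not rest on them. It is confined to the exploratory secondary Cox models. PFS-6, both stages of the efficacy rule and toxicity stopping are unaffected, as are the Kaplan-Meier curves if drawn from unaltered times.

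**What to change.** In 9.3, replace the random-subtraction phrase with a statement that ties will be handled by Efron's method, or by the exact partial likelihood, which is feasible with 27 patients, and that observed times are left unaltered. This removes the seed dependence whatever time unit is used, and it also removes the ambiguity about same-day censoring.

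Both are standard methods and need no new data, patients or procedures. Section 10.7 requires IRB approval, and review and approval by the drug supplier, before an amendment is implemented. The sensible course is to make this wording change at the next amendment rather than open one for it.

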10.0 STUDY MANAGEMENT

10.1 Conflict of Interest

Any investigator who has a conflict of interest with this study (patent ownership, royalties, or financial gain greater than the minimum allowable by their institution, etc.) must have the conflict reviewed by their own institution's COI committee. All investigators will follow the University conflict of interest policy.

11.2 Institutional Review Board (IRB) Approval and Consent

It is expected that the IRB will have the proper representation and function in accordance with federally mandated regulations. The IRB should approve the consent form and protocol.

In obtaining and documenting informed consent, the investigator should comply with the applicable regulatory requirement(s), and should adhere to Good Clinical Practice (GCP) and to ethical principles that have their origin in the Declaration of Helsinki.

Before recruitment and enrollment onto this study, the patient will be given a full explanation of the study and will be given the opportunity to review the consent form. Each consent form must include all the

relevant elements currently required by the FDA Regulations and local or state regulations. Once this essential information has been provided to the patient and the investigator is assured that the patient understands the implications of participating in the study, the patient will be asked to give consent to participate in the study by signing an IRB-approved consent form.

Prior to a patient's participation in the trial, the written informed consent form should be signed and personally dated by the patient and by the person who conducted the informed consent discussion.

10.3 Required Documentation (for multi-site studies)

Before the study can be initiated at any site, the following documentation must be provided to UCI CFCCC.

- A copy of the official IRB approval letter for the protocol and informed consent
- IRB membership list
- CVs and medical licensure for the principal investigator and any associate investigators who will be involved in the study
- Form FDA 1572 appropriately filled out and signed with appropriate documentation
- Financial Disclosure statements for the PI and participating investigators, as necessary
- A copy of the IRB-approved consent form and HIPAA form
- IRB member list with their occupations and institutional affiliations or a general assurance number will be acceptable.
- CAP and CLIA Laboratory certification numbers and institution lab normal values
- Signed protocol signature page

10.4 Data Completion

10.4.1 OnCore Date Entry

Data, as indicated by Sponsor, will be entered into OnCore – UC Irvine's Clinical Trial Management system. The Investigator is responsible for ensuring all entries are accurate and correct. The Investigator must maintain accurate source data that support OnCore data entry. All data will be entered as per Sponsor's specification and timeframe.

10.4.2 Recording of Events

All investigator initiated treatment trials require that adverse events, serious adverse events, deviations, and unanticipated problems be entered into the clinical trial management system (CTMS), OnCore. All entries must be entered in OnCore within the timelines specified in sections 7.5-7.6 of being aware of the adverse event, serious adverse event, violation, deviation, or unanticipated problem. Adverse events and violations/deviations and adverse events that are unanticipated problems that require prompt reporting to the DSMB must be entered into OnCore according to the timelines as specified in section 7.4-7.6.

10.5 Data Management and Monitoring/Auditing

10.5.1 Quality Assurance

Quality assurance activities will be conducted as per UC Irvine Chao Family Comprehensive Cancer Center's Quality Assurance Monitoring and Auditing Plan and at the discretion of the CFCCC Data and Safety Monitoring Board in order to ensure patient safety and data integrity oversight. By conducting internal monitoring and auditing, the CFCCC will ensure compliance with high quality standards and all applicable regulations, guidelines, and institutional policies. Trial monitoring and auditing may be completed remotely or on-site by the Quality Assurance

Officer. Participating sites may follow their own internal quality assurance policies in order to maintain patient safety and data integrity oversight. The investigator must permit study-related monitoring/auditing and provide access to study-related materials.

10.5.2 Data and Safety Monitoring Plan

This is a **risk level 2 study**, as defined in the Chao Family Comprehensive Cancer Center (CFCCC) Data and Safety Monitoring Plan (DSMP) because it is a study in which the IND is exempt by the FDA.

The Principal Investigator (PI), co-investigator, clinical research coordinator, and statistician are responsible for monitoring of data and safety for this study. For studies that have stopping rules for safety and efficacy, the PI will be responsible for the implementation and make changes as applicable. The CFCCC Data and Safety Monitoring Board (DSMB) is an independent body responsible for the safety of study subjects as well as the data integrity of the protocol. Data and safety will be reported to the DSMB with submission of progress reports that include aggregated reports of adverse events, serious adverse events, deviations, and violations. In addition, certain adverse events, serious adverse events, deviations, violations, and unanticipated problems will be reported promptly to the DSMB for review according to Section 7.4 and Section 7.5.

10.6 Adherence to the Protocol

Except for an emergency situation in which proper care for the protection, safety, and well-being of the study patient requires alternative treatment, the study shall be conducted exactly as described in the approved protocol.

Due to restrictions instituted during the COVID-19 pandemic, planned clinic visits may be performed via telemedicine at the discretion of the Principal Investigator, following the guidelines established in the CFCCC Standard Operating procedure "Interim Standard Operating Procedure: Clinical Trial Enrollment and Operations during the COVID-19 Pandemic" (URL: \hs.uci.edu\myshare\Cancer Center Research\COVID-19\Research\SOPs and Guidelines). Whenever possible, on-site clinic visits will be replaced by telemedicine visits between the clinic staff and on-study patients.

Emergency Modifications may be enacted if needed to ensure the safety, and well-being of the study patients. Investigators may implement a deviation from, or a change of, the protocol to eliminate an immediate hazard(s) to trial subjects without prior IRB approval. For any such emergency modification implemented, an IRB modification form must be completed within five (5) business days of making the change.

All other planned deviations or violations from the protocol must have prior approval by the Principal Investigator and the IRB. Please refer to Section 7.4 for more information on how protocol deviations and violations are defined. It will also provide instructions on when and who to contact and obtain approval from for prospective deviations. Protocol deviations should also be reported in accordance with UCI IRB, UCI CFCCC Stern Center policies and the participating site's IRB policies.

10.7 Amendments to the Protocol

Should amendments to the protocol be required, the amendments will be originated and documented by the Principal Investigator. It should also be noted that when an amendment to the protocol substantially alters the study design or the potential risk to the patient, a revised consent form might be required. Protocol modifications or amendments must be reviewed and approved by Exelixis prior to implementation.

The written amendment, and if required the amended consent form, must be sent to the IRB for approval prior to implementation.

10.8 Record Retention

Study documentation includes all Case Report Forms, data correction forms or queries, source documents, Sponsor-Investigator correspondence, monitoring logs/letters, and regulatory documents (e.g., protocol and amendments, IRB correspondence and approval, signed patient consent forms).

Source documents include all recordings of observations or notations of clinical activities and all reports and records necessary for the evaluation and reconstruction of the clinical research study.

Government agency regulations and directives require that the study investigator must retain all study documentation pertaining to the conduct of a clinical trial. In the case of a study with a drug seeking regulatory approval and marketing, these documents shall be retained for at least two years after the last approval of marketing application in an International Conference on Harmonization (ICH) region. In all other cases, study documents should be kept on file until three years after the completion and final study report of this investigational study.

